All Veterans enrolled in the study will be beginning a course of either Prolonged Exposure (PE) or Cognitive Processing Therapy (CPT), which will be delivered as usual by PTSD clinical staff. As the BFI is an adjunctive intervention, Veterans' trauma-focused treatment is considered separate from the present study. The Veterans will be seen by regular clinical staff and no artificial limits will be imposed upon their treatment, although treatment engagement will be tracked (see Assessment section, below). Veterans and their family members will be recruited for the present study at the beginning of a course of treatment at the clinic. Phase I will be an open pilot trial of 4 dyads. All family members in Phase I will receive the BFI, which will be delivered as 2 weekly 50-minute sessions of the BFI, consistent with the application with the BFI in previous work (Thompson-Hollands et al., 2015). Phase II will include 20 dyads (N=40) using identical recruitment, inclusion/exclusion criteria, and assessment structure; however, in this second phase family members will be randomly assigned to receive or not receive the BFI, and VABHS clinicians will deliver the BFI sessions (rather than the PI as in Phase I).

Veterans:

Inclusion criteria.

- (1) has a current diagnosis of PTSD

(2) is 18 years of age or older

(3) has an eligible family member (defined as a spouse/significant other, parent, adult child, sibling, etc., 18 years of age or older who currently has substantial daily or weekly contact with the Veteran)

(4) is beginning a course of either CPT or PE at VA Boston.

Exclusion criteria.

(1) has current diagnoses of unstable bipolar disorder, past or present psychosis, or organic mental disorder

(2) has clear and current suicidal risk (assessed via the MINI-Suicide Module (Sheehan et al., 1998), see Assessment section below)

(3) has current moderate or severe substance use disorder

(4) is currently participating in family-based therapy/couples-counseling

Family members:

Inclusion criteria.

(1) is 18 years of age or older

(2) is the family member (defined as a spouse/significant other, parent, adult child, sibling, etc.) of the Veteran

(3) currently has substantial daily or weekly contact with the Veteran

Exclusion criteria.

(1) has a current diagnosis of PTSD

(2) has current diagnoses of unstable bipolar disorder, past or present psychosis, or organic mental disorder

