During the pilot *Phase I* the PI will serve as the BFI clinician. The PI has considerable clinical experience in the treatment of Veterans with PTSD. Additionally, as described above, the PI designed the BFI and has successfully tested its efficacy in a study of patients with OCD and their family members. Beginning in *Phase II* the PI will no longer deliver the intervention; instead, a minimum of 3 clinicians from the VABHS PTSD clinic will be recruited and trained to deliver the BFI.

Comparison condition: Family members in the control or comparison condition of *Phase II* will not receive the BFI or any other study-specific family sessions (aside from the assessments described below). In keeping with the effectiveness aims of the present study, family members in the comparison condition (and the BFI condition) will not be prohibited from receiving any family-inclusive services or sessions that would normally be offered to them in the context of usual VA care.

Independent variables: Receiving or not receiving the BFI (for Veterans/family members); receiving or not receiving training in the BFI (for clinicians).

Dependent variables: Treatment engagement and PTSD symptoms (for patients); accommodation and active treatment support (for family members); qualitative feedback and rates of participation (for Veterans, family members, and clinicians).

Assessment:

Measures and assessment points are shown in Table 1. Qualitative interviews with stakeholders (Veterans, family members, and clinicians) will continue throughout both Phases of the study, as described below. Clinician-rated assessments of Veterans and family members will be completed (in person or via telephone/mail, or a combination of in person and remotely) at baseline and weeks 6, 12, and 16; Veterans and family members will be compensated \$50 for each of these 4 assessment visits that they complete (total of \$200 for the major assessments). Finally, PE and CPT therapists will complete ratings of Veterans' treatment engagement at each session, and will monitor dropout.

Table 1. Assessment Measures and Timepoints

	Time of Administration					
	Baseline	Weeks 0-6	Every PE/CPT session	Week 6	Week 12	Week 16
CAPS-5	X ^v			X ^v	X ^v	X ^v
SCID-5	X ^{v, f}					
Demographics form (Vet/FM)	X ^{v, f}					
Demographics form (Clin)	X ^{tx}					
Relationship information form (Vet)	X ^v					
Relationship information form (FM)	X ^f					
LEC-5	X ^{v, f}					
WTAR	X ^{v, f}					
MOCA	X ^{v, f}					

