The Beck Anxiety Inventory (BAI) (Beck et al., 1988)

The Inventory of Psychosocial Functioning (IPF-80) (Bovin et al., 2018) will be used to index objective role functioning/impairment in the following domains: romantic relationship, family, parenting, work, friendships and socializing, education, and self-care

PTSD Checklist-5 (PCL-5) (Weathers, Litz, Huska, & Keane, 1994)

Revised Conflict Tactics Scale (CTS-2) (Straus, Hamby, Boney-McCoy, & Sugarman, 1996)

Posttraumatic Avoidance Behavior Questionnaire (PABQ) (van Minnen & Hagenaars, 2010)

Posttraumatic Cognitions Inventory (PTCI) (Foa, Ehlers, Clark, Tolin, & Orsillo, 1999)

At each PE or CPT session, the Veteran's therapist will complete (1) a record of session attendance (or dropout, if applicable), along with (2) the Homework Compliance Scale (Leung & Heimberg, 1996) (HCS).

Family member-specific assessments:

Family members will complete/be assessed using the following previously described measures, as outlined in Table 1:

SCID-IV

Demographics form

Relationship information form

AUDIT

LEC-5

WTAR

MOCA

MINI-Suicide module (only administered at follow-up if score was ≥ 1 at baseline, see DSMB section)

RDAS

PCS

MSPSS

DERS

BDI-II

BAI

IPF-80

CTS-2-SF

PCL-5 (family members will rate the PCL-5 based on their perception of the Veteran's current symptoms)

Family members will also complete the following (timing outlined in Table 1):

Significant Others' Responses to Trauma Scale (Fredman et al., 2014) (SORTS)

Caregiving Appraisal Scale (Lawton, Moss, Hoffman, & Perkinson, 2000)

Involvement in Therapy Checklist (ITC). This measure consists of a checklist of involvement in the Veteran's treatment since the last assessment (assisting with therapy homework, driving patient to appointments, attending therapy sessions with the Veteran, etc.).

Treatment Expectancy Questionnaire (TEQ; Borkovec & Nau, 1972). The TEQ will be administered immediately after the first BFI session. Wording was modified slightly to better describe the family program.

The therapeutic alliance following the BFI will be assessed using the 12-item therapist and client versions of the Working Alliance Inventory (WAI; Horvath & Greenberg, 1989; Tracey & Kokotovic, 1989). Wording was modified slightly to better describe the family program.

The Client Satisfaction questionnaire (CSQ) will assess family members' satisfaction with the overall program.

Clinician-specific assessments:

Demographics form

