Overview of data analysis: Quantitative data analysis will be performed using MPlus and SPSS, and NVivo management software will be used for qualitative data. Prior to full data analysis, the balance of randomization will be checked and unbalanced factors between groups will be controlled for in subsequent analyses. Similarly, all major variables will be assessed for skewness and outliers, and in cases where parametric analytic assumptions are violated we will use transformations. Preliminary analyses will consist of descriptive statistics by assessment period. All quantitative outcomes will be tested at a two-sided $\alpha=.05$ level.

Data checking: Standard data checking procedures will include checking forms for missing data, double entry with discrepancy resolution, daily back-up copies of computer files, and examination of key variables for skewness, variability, missing data, and outliers. Data will be transformed to achieve normality if needed. If any outcome variable is too zero-inflated to allow for transformation, it will be analyzed with logistic regression or generalized estimating equation techniques (appropriate for this small pilot study).

Missing data: We will make every effort to retain participants, but as treatment engagement is a key outcome of the present study we will also carefully tabulate and report dropout rates and patterns in the present study, including exact timing of dropout. Multilevel regression models will be used to evaluate treatment outcomes; this approach is robust to missing data and is considered "state of the art" for use with unbalanced data sets due to treatment dropout (Schafer & Graham, 2002). There are also several methods for correcting biases due to missing data when using a multilevel regression approach (e.g., pattern-mixture modeling).

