Hypothesis 1 analytic strategy: We will examine the feasibility and acceptability of the BFI by examining rates of BFI recruitment and refusal, as well as level of drop-out from the BFI sessions. These data will be benchmarked to previous BFI efficacy data. We will also assess the success of the clinician training program by reviewing rates of clinician recruitment and attitudes reported on the EBPAS-50. Furthermore, we will conduct detailed in-person, semi-structured exit interviews with Veterans, family members, and clinicians in order to collect qualitative data. These data will allow us to contextualize our findings related to the protocol's fit in this novel setting and its acceptability to Veterans, families, and providers. The qualitative interviews will provide more nuanced feedback regarding the perceived fit of the BFI, and further identify necessary modifications to the protocol (see below for qualitative analytic strategy).

Aim 2: Assess the BFI's effects on symptoms as well as potential mechanisms of change using multilevel modeling.

Hypothesis 2a: Veterans whose family members receive the BFI will show lower levels of PTSD symptoms at post-treatment and greater engagement throughout treatment compared to control Veterans.

Hypothesis 2b: Family members who receive the BFI will show more active support for treatment and less accommodation than control family members.

Hypothesis 2c: Family members' active support for treatment will be positively related to Veterans' treatment engagement, and Veterans' levels of perceived criticism will be negatively related to their treatment engagement

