Hypothesis 2a-2c analytic strategy: Multilevel regression (i.e., hierarchical linear modeling (HLM), growth curve analysis, etc.) will be used to evaluate change in continuous outcome variables (Singer & Willett, 2003). Multilevel regression is a robust method for analyzing change over time, with excellent options for handling missing data, powerful estimation abilities, and flexibility of modeling. This approach will allow for the analysis of an intent-to-treat sample in line with CONSORT guidelines (Altman et al., 2001). For our analysis of change in the variables of interest we will use a multilevel framework in the Mplus program to model time as a Level 1 predictor of the outcome variables (baseline and weeks 6, 12, and 16). We will first specify an unconditional model to ascertain the shape of the change trajectories (e.g., linear versus quadratic change over Time), and will subsequently specify conditional multilevel models to examine treatment effects and the impact of other variables as predictors of individual differences in change. We will also calculate the Cohen's *d* effect size and 95% confidence intervals in order to provide a benchmark for future trials.

o. Literature Cited

Aarons, G. A., Cafri, G., Lugo, L., & Sawitzky, A. (2010). Expanding the domains of attitudes towards evidence-based practice: The Evidence Based Practice Attitude Scale-50. *Administration and Policy in Mental Health and Mental Health Services Research*, 39(5), 331–340. <http://doi.org/10.1007/s10488-010-0302-3>

Boeding, S. E., Paprocki, C. M., Baucom, D. H., Abramowitz, J. S., Wheaton, M. G., Fabricant, L. E., & Fischer, M. S. (2013). Let me check that for you: symptom accommodation in romantic partners of adults with Obsessive-Compulsive Disorder. *Behaviour Research and Therapy*, 51(6), 316–322. <http://doi.org/10.1016/j.brat.2013.03.002>

Borkovec, T.D., & Nau, S.D. (1972). Credibility of analogue therapy rationales. *Journal of Behavior Therapy and Experimental Psychiatry*, 3, 257-260.

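### The family-support checklist (ITC) has look-back windows of 6, 6 and 4 weeks and no baseline score, so the planned change-over-time model partly reads window length as change in support

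*Combined protocol and SAP*

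**What the plan says.** - **Hypothesis (Aim 2, Hypothesis 2b):** "Family members who receive the BFI will show more active support for treatment and less accommodation than control family members". The paragraph on dependent variables also names active treatment support as an outcome for family members.
- **Instrument (Family member-specific assessments):** the ITC is described as follows: "This measure consists of a checklist of involvement in the Veteran's treatment since the last assessment". The examples given are help with therapy homework, driving to appointments and attending sessions. No scoring rule, fixed recall period or denominator is stated.
- **Schedule (Assessment, Table 1):** assessments take place "at baseline and weeks 6, 12, and 16". In Table 1 the ITC is marked for family members at weeks 6, 12 and 16 only. The SORTS, which measures accommodation, is also marked at baseline.
- **Model (Hypothesis 2a-2c analytic strategy):** the plan is "to model time as a Level 1 predictor of the outcome variables (baseline and weeks 6, 12, and 16"). It adds: "We will first specify an unconditional model to ascertain the shape of the change trajectories". Conditional models for treatment effects follow, then Cohen's d with 95% confidence intervals. Nothing specific to the ITC is given: no offset, no rate and no rule for a missed visit.
- **Testing and size:** under Overview of data analysis, "All quantitative outcomes will be tested at a two-sided" level of 0.05. Under Work Proposed, "Phase II will include 20 dyads (N=40"), half of whose family members receive the BFI.

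**The concern.** A checklist that looks back to the previous assessment covers as much time as has passed since that assessment. Here the last scheduled window is a third shorter than the first two. A growth model on calendar time has no means of separating less support per week from fewer weeks asked about. The unconditional model that chooses between linear and quadratic change would take in the same artefact.

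The timing of the BFI adds a second problem. It consists of two weekly sessions at the start of the Veteran's treatment, so the first ITC score, at week 6, will normally already carry much of any early effect. With no earlier score, that part of the effect lies in the level. A model aimed at change can understate or miss a benefit that starts early and persists, which is a plausible pattern for this intervention.

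**Working it through.** The documents give no effect size, power figure or scoring for the ITC, so there is no stated figure to reproduce. The rates and scoring below are assumptions.

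**Windows.** From the visit weeks: 6 - 0 = 6, 12 - 6 = 6, 16 - 12 = 4 weeks. If the last assessment means the last one completed, missing week 6 makes the week-12 window 12 weeks (12/6 = 2 times the planned length). Missing week 12 makes the week-16 window 10 weeks (10/4 = 2.5 times).

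**Count scoring, constant rate r per week.** Expected scores are 6r, 6r and 4r. Week 16 is 4/6 = 67% of week 6, a 33% fall with no change in support. A true 50% rise in weekly support by week 16 gives 1.5r × 4 = 6r, which looks flat.

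**Slope of the artefact.** The mean of weeks 6, 12 and 16 is 11.33, with deviations -5.33, 0.67 and 4.67 (sum of squares 50.67). The cross-product with windows 6, 6, 4 is -32 + 4 + 18.67 = -9.33. The slope is -9.33/50.67 = -0.184r per week.

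**Between arms, counts.** The artefact in the arm-by-time term is (BFI rate - control rate) × (-0.184).
- Equal rates: 0. The artefact cancels.
- Rates 1.5 and 1.0: scores are 9, 9, 6 and 6, 6, 4, and the differences are 3, 3, 2. The term is 0.5 × (-0.184) = -0.092 per week, against the BFI, although its advantage per week never changes.
- Log scale: ln(4/6) gives a slope of -0.037 per week in each arm, which cancels.

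**Between arms, yes/no items.** Take 10 items (assumed), each with expected score 1 - exp(-item rate × window). Across control item rates of 0.05 to 0.5 per week and rate ratios of 1.5 and 2, scores fall at week 16 in both arms, and the arm-by-time term runs from -0.040 to +0.064 per week. The sign is therefore not fixed.

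**Simulation for counts.** 10 per arm, Poisson counts, between-person coefficient of variation 0.5 (assumed), complete data, 20,000 runs, two-sided 0.05. The arm-by-time test is a t-test on per-person slopes.

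| Control rate | Rate ratio | Arm-by-time rejected, raw | Of which against BFI | Arm-by-time, divided by weeks | Mean level rejected, raw / divided |
|---|---|---|---|---|---|
| 1 | 1 | 4.9% | 2.4% | 5.1% | 4.9% / 4.7% |
| 1 | 1.5 | 7.5% | 6.8% | 5.2% | 31.9% / 32.1% |
| 2 | 1.5 | 10.1% | 9.6% | 5.0% | 35.2% / 35.3% |
| 1 | 2 | 14.6% | 14.4% | 4.8% | 73.7% / 73.7% |
| 2 | 2 | 22.4% | 22.3% | 5.2% | 77.1% / 76.5% |

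Within the control arm alone, a false change over time is declared in 34% of runs (r = 1) or 59% (r = 2). Dividing by weeks brings this to about 5%.

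**The case against.** Several points on the other side stand and limit the concern.

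- **Hypothesis 2b is worded as a level.** It says more support than controls, not a steeper slope. Scheduled windows are the same in both arms, so window length alone creates no arm difference and no excess type I error. In the example the BFI arm stays ahead at every visit. The mean-level test keeps its sign and essentially all its power.
- **The slope is not named as the only test.** The strategy speaks of treatment effects generally and adds Cohen's d. A reader might infer that the planned test of 2b would come out reversed when the BFI works. The documents do not support that. What they show is that the contrast for the ITC is left open within a model of change.
- **The slope may hold part of the effect.** A reader might infer that the week 6-16 slope cannot contain the BFI effect. That goes too far: the first window can mix time before and after the sessions, and support can grow or fade later.
- **Scoring is unknown.** Frequency ratings would be largely immune.
- **The missing baseline is largely structural.** Dyads enrol as PE or CPT begins, so there is little involvement in that course to report. The fault is that the model assumes a baseline, not that none is collected.
- **Unequal missed visits are speculative.** Assessments may be done by telephone or mail, and staff pursue incomplete ratings. Nothing suggests that completion differs by arm.
- **Support depends on sessions taking place.** CPT is defined as 12 sessions and PE as at least 8. If sessions are roughly weekly (an assumption), treatment may have ended for some during weeks 12-16, and support would fall for that reason under any look-back.

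These points leave intact the distortion of the time trend, of the trajectory shape and, when the arms truly differ, of the arm-by-time term.

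**Conclusion.** The concern holds in a limited form. As written, the plan applies a model of change from baseline to a measure that has no baseline score and unequal look-back windows. Under count or ever-done scoring, the time trend and the linear-versus-quadratic choice partly reflect window length. For a count at a constant rate the false fall is 33% at week 16. When the BFI has a constant benefit, the arm-by-time term is distorted: -0.092 per week against the BFI for raw counts at assumed rates of 1.5 and 1.0, and in either direction for yes/no items. An early, sustained benefit may lie mainly in the level and be understated by a slope.

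All sizes rest on assumed rates and scoring. Severity is minor to moderate: the study describes itself as preliminary, and the Data Monitoring Plan lists CAPS-5, homework ratings and attendance/dropout as primary outcomes, not the ITC.

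**What to change.** 1. **State the scoring** of the ITC.
2. **Use the same fixed look-back at every visit**, for example the past 4 weeks, which fits inside all three intervals and works for any scoring.
3. **For data already collected**, record the weeks since the last completed ITC. Use them as an offset or divisor if the score is a count. If items are yes/no, use them as a covariate; dividing is not valid there, because such items do not accrue in proportion to time.
4. **Name the contrast.** Test the support part of Hypothesis 2b as the between-arm difference in mean ITC level over weeks 6, 12 and 16, within the multilevel framework, with visit as a categorical factor and no baseline term. Do not use a slope or a change from baseline.
5. **Optionally, report support per attended session** as a description, since attendance is recorded. It should not replace the main contrast: attendance is itself something the BFI is meant to raise, so a per-session rate answers a different question.

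The cost is one line on the form and a few sentences in the analysis plan. The downside is that a 4-week look-back leaves the first 2 weeks of each 6-week interval unreported. The document is dated July 2021 and enrolment was expected from winter 2016/2017, so item 3 may be the part that applies to most of the data.

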1. We will carefully screen to identify individuals whose risk for potential adverse outcomes is elevated were they to participate in the proposed research. Such individuals will be excluded from the study. As an

example, an actively suicidal person would be excluded from study participation and appropriate clinical treatment or referrals provided.

2. Clinical staff will be trained to cope with any anxiety/distress experienced by participants during the assessments and intervention. Staff will also monitor assessment items that ask about risk of suicide or current domestic violence at each timepoint. These items will be reviewed immediately upon completion, and participants who endorse elevated risk of suicide or current domestic violence will meet with the PI for further assessment. See Section 5b ("Safety monitoring plan") below for details of the standard procedure for suicidal risk. For current domestic violence, the PI (in consultation with a licensed clinical supervisor on site) will assess risk and provide the participant with clinical and community referrals as needed.

3. Careful monitoring of participants during study participation will be conducted by the project staff. Participants will be monitored for any increase in symptoms as the study progresses. Each participant will see the same clinician for each of their treatment or intervention visits (in the case of Veterans, their same usual care clinician. In the case of family members, the same BFI clinician), and the same assessor for each assessment occasion when appropriate. Following the clinical trial policy of the VA Boston Healthcare System, all participants will be given an emergency number to call in case of an emergency. This number will be the psychiatry on call system of the VA Boston Healthcare System.

4. Participants will be instructed to contact study personnel at any time (including during the follow-up period) in the event of worsening symptoms. Participants whose clinical condition has deteriorated will be removed from the study and given appropriate clinical care. See DSMP for details.

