b. Safety Monitoring Plan. In the proposed study we will use the FDA definition of adverse events (AE) and serious adverse events (SAE). Any SAE, whether or not related to the study intervention, will be reported immediately to the IRB. In the event that a participant either withdraws from the study or the PI decides to discontinue a participant due to an SAE, the participant will be monitored by the PI via ongoing status assessment until (a) a resolution is reached (e.g., the problem has resolved or stabilized with no further change expected), (b) the SAE is determined to be clearly unrelated to the study intervention, or (c) the SAE results in death. Outcomes of SAEs will be regularly reported to the IRB. A summary of the SAEs that occurred during the previous year will be included in the annual IRB renewal. Suicidal ideation and AEs will be formally assessed at baseline and at all other assessment visits (see below for detailed information regarding assessment of suicidal ideation).

Participants will be informed that the interim results of the study will not necessarily be revealed to them, even if there is a suggestive trend in favor of the treatment, so as to maintain the scientific integrity of the study(Slutsky & Lavery, 2004). During the first in person screening, potential participants will undergo a comprehensive screening to determine their eligibility for, and safety for, participation in the study. Attention will

be paid to current suicidal ideation. Individuals who report imminent risk will be excluded from participation in the study and will be provided with appropriate clinical referrals.

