Additionally, if at any point during the study (either baseline or follow-up) a participant describes a clear intent or inability/unwillingness to develop and follow a Suicide Prevention Safety Plan, which is a VA standard of care, then they will be terminated from the study and the crisis will be managed. Specifically, staff will immediately locate [name], who is a licensed psychologist, or another licensed psychologist, who will follow standard VA suicide prevention and risk management procedures. A licensed clinical psychologist will always be on-site when assessments are conducted. The psychologist will intervene by (a) following up with direct questions about suicidal behaviors, (b) assessing mental status by asking about psychotic symptoms, mood symptoms, and drug and alcohol use, (c) scheduling extra contacts if necessary, emphasizing problem solving, (d) helping the participant to generate short-term objectives, and (e) collaboratively developing or refining a Safety Plan using the VA's comprehensive Safety Planning template and manual. The plan will address what actions need to be taken in the succeeding days to solve the problems that precipitated suicidal behavior. The plan will also address the use of voluntary and involuntary hospitalization, if necessary. In addition to these formal assessments, all participants will be given the number of the on-call psychiatry service at VA Boston Healthcare System and informed that they should call this number after normal business hours in the event that they are feeling suicidal and/or distressed, as well as the National Suicide Prevention hotline number, which is a 24-hour service with a specific line dedicated to Veterans. During business hours the participants will be instructed to contact the PI. Should a participant call to indicate suicidal risk, then the previously described intervention plan will be followed. All Veterans in the study will also be under non-study care through the VABHS, and will be monitored as appropriate by their individual clinicians.

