Veteran participants will be administered the MINI-Suicide module at baseline and at each follow-up assessment. Family members will be administered the MINI-Suicide module at the baseline assessment; those family members who score a 0 at baseline on the MINI-Suicide module will not be reassessed at future follow-up points. However, any family members that score ≥ 1 baseline will continue to have the MINI administered at follow-up assessments to monitor risk. If at any point during these follow-up assessments a family member indicates that they are experiencing high levels of suicidal thoughts, study staff will proceed with the steps outlined above (e.g., further assessment by a licensed psychologist of the intensity of thoughts, assessment of any related behaviors, collaborative completion of a Safety Plan, scheduling of additional contacts in the near term, and/or potentially a voluntary or involuntary hospitalization, as determined by the licensed psychologist).

In the event that a participant experiences high distress (i.e. exacerbated symptoms) but without any suicidal ideation or threat, then the PI will intervene by asking direct questions about the nature and causes of the distress, conduct a symptom assessment, and schedule extra contacts (assessments) and/or work closely with the patient's other VA providers if deemed necessary. Veterans' PTSD care will not be constrained or limited in any way by their participation in the study; therefore, their individual clinicians will be free to make any appropriate treatment decisions in response to increased distress, including seeking hospitalization or another higher level of care, discontinuing PE/CPT and instead conducting supportive or crisis-oriented therapy, etc. Any such changes in treatment focus will be monitored and reported to the IRB as appropriate.

DATA ANALYSIS.

Data management: All clinician-administered and self-report questionnaire data will be entered into the database by the Research Assistant (RA) on the same day of administration to ensure completeness. All data will be cleaned and rechecked for accuracy before being exported into the appropriate program (e.g., SPSS, MPlus, and NVivo) for analysis. Data collected via mEMA will be continuously available via the secure cloud-based storage system and accessible via a unique access site available only to study staff.

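### The protocol removes participants who deteriorate, the safety plan it cites keeps most of them, and neither says the CAPS-5 continues after removal

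*Combined protocol and SAP*

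**What the plan says.** **The removal rule.** Human Studies Section, 2b (Protection against risk), item 4: "Participants whose clinical condition has deteriorated will be removed from the study and given appropriate clinical care". The next sentence is "See DSMP for details". No measure, threshold or decision-maker is named.

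**What the DSMP says.** Section 5 gives two grounds for ending participation after enrolment.
- Under 5b.1, for clear suicidal intent, or inability or unwillingness to make and follow a Safety Plan: "then they will be terminated from the study and the crisis will be managed".
- Under 5b, where "the PI decides to discontinue a participant due to an SAE". After that, "the participant will be monitored by the PI via ongoing status assessment until" the event resolves, is found to be unrelated, or ends in death. No outcome measure is mentioned.

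For exacerbated symptoms without suicidality, 5b.1 has the PI enquire into the cause, assess symptoms and arrange extra contacts. Clinicians may change the Veteran's therapy, and "Any such changes in treatment focus will be monitored and reported to the IRB as appropriate". Nobody is removed on this ground.

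**What the plan says about follow-up and analysis.** Section 4 (Work Proposed) keeps Veterans who choose to stop PE or CPT in the study for follow-up. Section 5a lists the CAPS-5 total among the primary outcomes. The analytic strategy for Hypotheses 2a-2c aims at an intent-to-treat analysis by multilevel regression on baseline and weeks 6, 12 and 16.

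**The concern.** A Veteran whose symptoms worsen without suicidality is removed under item 4 and retained under the DSMP that item 4 cites. Staff have to infer which rule governs.

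Whichever they choose, the documents do not say whether a removed participant's CAPS-5 is still collected. If it is not, follow-up ends because of the outcome being measured. When worsening comes to light between visits and removal precedes the next rating, the missing score depends on its own unobserved value. A multilevel model fitted to the observed scores does not correct that. More removals would be expected in the arm doing worse, so a true difference in either direction would shrink toward zero. That undercuts the intent-to-treat aim.

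Removal also protects few people. Control families receive no study sessions, and BFI families enter follow-up after two. The Veteran's PE or CPT is separate from the study, and under 5b.1 "PTSD care will not be constrained or limited in any way by their participation in the study". For controls, and for BFI dyads once the two sessions are done, removal therefore stops only the assessments, which include the study's scheduled suicide-risk checks.

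**Working it through.** **Step 1: does any text continue the CAPS-5 after removal?** There are four candidates.
- Section 4 retains Veterans who choose to stop PE or CPT. It does not cover people whom the study removes.
- Section 5b's monitoring after an SAE is safety follow-up and names no outcome.
- Human Studies 1a offers a debriefing at early withdrawal and nothing more.
- The Missing data paragraph promises effort at retention and a report of dropout timing. It does not address removed participants.

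None continues the CAPS-5. Item 4 also covers family members, and the plan does not say whether the Veteran's CAPS-5 continues if the relative is removed.

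**Step 2: can the worse score be lost?** Yes. Item 4 itself invites participants to contact staff at any time about worsening, so deterioration can surface before the next scheduled rating. If it is found at a visit and rated there, the model uses that score.

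**Step 3: how large could the bias be?** The plan contains no figure to reproduce, so this is an illustration.

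From the documents: visits at weeks 0, 6, 12 and 16; 20 randomised dyads, half to BFI, so 10 per arm; two-sided 5% tests.

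Assumed:
- control change of -10 or -14 points by week 16, linear in time
- SD of week-16 change of 10, 12 or 14 (random intercept SD 9, residual SD 5, random slope set to match)
- arm difference of -6, 0 or +6
- removal at the first visit with CAPS-5 at least 10 points (or 5) above baseline, as a proxy for worsening noticed between visits
- the triggering score lost for all, half or none of those removed

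The data were simulated with 1,000,000 per arm per scenario (Monte Carlo error about 0.02 points). They were analysed with a maximum-likelihood growth model with random intercept and slope, and the standard error (SE) was scaled to 10 per arm.

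| Trigger | Triggering scores lost | True 6-point benefit estimated as | True 6-point harm estimated as |
|---|---|---|---|
| +10 | all | 5.09 to 5.76 | 4.59 to 5.46 |
| +10 | half | 5.54 to 5.89 | 5.31 to 5.70 |
| +10 | none | 5.97 to 6.01 | 5.97 to 6.01 |
| +5 | all | 4.48 to 5.38 | 3.86 to 4.84 |
| +5 | half | 5.28 to 5.69 | 5.06 to 5.44 |

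Attenuation is (6 - estimate)/6. With the +10 trigger and all scores lost:
- benefit: (6 - 5.76)/6 = 4% to (6 - 5.09)/6 = 15%
- harm: (6 - 5.46)/6 = 9% to (6 - 4.59)/6 = 24%

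The SE in these scenarios is 4.05 to 5.83. Taken scenario by scenario, the bias is 0.06 to 0.16 SE (benefit) and 0.13 to 0.26 SE (harm). With half lost it is 0.03 to 0.08 and 0.07 to 0.12 SE. With the +5 trigger and all lost it reaches 0.27 and 0.41 SE. With no true difference the bias stays within 0.03 points.

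Coverage of a 95% interval with bias r SEs is Φ(1.96 - r) - Φ(-1.96 - r). At r = 0.26 this is Φ(1.70) - Φ(-2.22) = 0.955 - 0.013 = 94.2%. At r = 0.41 it is Φ(1.55) - Φ(-2.37) = 0.939 - 0.009, about 93%.

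With the +10 trigger, expected removals among 20 Veterans are 0.5 to 1.8 (benefit) or 1.2 to 3.4 (harm).

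**The case against.** The strongest reply is that item 4 is a one-line summary that defers to the DSMP, and the DSMP deals with this very case without removing anyone. The broad reading also sits badly with the rest of the protocol. BFI clinicians tell relatives that a modest, passing rise in intrusive thoughts early in therapy is a good sign, and Veterans who stop therapy stay in follow-up. The Missing data paragraph promises effort at retention and mentions pattern-mixture modelling. Bias needs three things together: item 4 applied literally, removal before rating, and a true arm difference. Every simulation input is assumed, only the broad reading was simulated, and the trial calls itself preliminary. Finally, seeking research data from someone terminated in a suicidal crisis is a clinical judgement, not a matter of wording.

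Much of this stands. The DSMP-governed reading is plausible, the size is small, and assessment after a crisis must depend on clinical acceptability. Two things remain. The text allows the broader rule and leaves staff to infer the narrower one. And even on the narrow reading nothing keeps the CAPS-5 going after a suicidal crisis or an SAE discontinuation. Pattern-mixture modelling is named only as an available method, and the retention promise does not reach people whom the study itself removes.

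**Conclusion.** The point holds, at minor severity. The two removal rules conflict as written, and collection of a primary outcome after removal is left unstated under both.

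Under the assumptions above, the worst case with a 10-point trigger is a 4 to 15% understatement of a 6-point benefit, or 9 to 24% of a 6-point harm, never more than 0.26 SE. If the worse score is rated before removal there is no bias. If the arms do not differ, bias is within 0.03 points. The narrow reading was not sized.

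This would not by itself change the conclusions of a 20-dyad pilot. The reason to act is that the correction costs little and removes a contradiction.

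**What to change.** Amend item 4 so that removal is limited to the DSMP's two grounds, and state that removal means stopping study intervention procedures only. Continue to seek the week 6, 12 and 16 assessments and the attendance data for every randomised dyad unless consent is withdrawn, remotely if needed and when clinically acceptable. This extends what section 4 already does for Veterans who stop PE or CPT. Say explicitly that the Veteran's CAPS-5 continues if only the family member is removed.

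Report removals by arm with reasons, and whether a CAPS-5 was obtained, within the dropout reporting already promised. That part remains possible if follow-up has finished, and it would inform the larger trial this pilot is meant to support. A pattern-mixture or poor-outcome sensitivity analysis is optional at this sample size.

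The cost is amendment wording and a few visits that are already scheduled. The downside is some contact burden for distressed participants, some of whom may decline.
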